### 2.2 Safety Analysis Set

The safety analysis set will include all eyes with attempted use of the UNITY VCS (successful or aborted after contact with the eye) and will be used for the safety outcomes. Attempted use of the UNITY VCS is defined as any time the device makes contact with the eye.

## 3 SUBJECT CHARACTERISTICS AND STUDY CONDUCT SUMMARIES

Subject characteristics and study conduct summaries will include subject disposition, demographics, and baseline cataract grade. Listings will be provided for medical history, screen failures by reason, protocol deviations, baseline medications, and for subjects included in the Safety analysis set but excluded from the All-Implanted analysis set. All descriptive summary statistics will be displayed with count and percent for categorical data, and with sample size (N), mean, standard deviation, median, minimum, and maximum for continuous data.

Subject characteristics and study conduct summaries will be presented for the all-implanted analysis set unless the safety analysis set is different, in which case they will be presented for both.

## 4 EFFECTIVENESS ANALYSIS STRATEGY

[figure not shown]
### 4.1 Effectiveness Endpoints:

Primary Endpoint

- From the surgeon questionnaire, which is completed after each subject surgery, the percentage of 'Yes' responses to the question: ***Did UNITY VCS using anterior segment surgical functionality perform per the intended use as defined in Protocol Section 5.1?***

#### Secondary Endpoint

- From the cataract surgery, time from incision entry to incision closure (seconds)

### 4.2 Effectiveness Hypotheses

No hypothesis testing will be performed. Analyses will be descriptive only.

### 4.3 Statistical Methods for Effectiveness Analyses

[figure not shown]
Standard descriptive statistics will be presented based on the type. Individual subject data listings will also be provided. No imputation of missing data is planned. The all-implanted analysis set will be used for all effectiveness analysis and all analyses will be based on the study eye unless otherwise stated.

#### 4.3.1 Analysis of the Primary Endpoint

After each surgery, the surgeon completes a user preference questionnaire. For subjects in the all-implanted analysis set, the rate of 'Yes' responses to the question ***Did UNITY VCS using anterior segment surgical functionality perform per the intended use as defined in Protocol Section 5.1?*** will be presented with a count and percentage and will be accompanied by a two-sided exact binomial 95% confidence interval.

#### 4.3.2 Analysis of the Secondary Endpoint

The time from incision entry to incision closure for the cataract surgery will be summarized for subjects in the all-implanted analysis set. The number of subjects, mean, median, standard deviation, minimum, and maximum will be reported. A two-sided 95% confidence interval based on the t-distribution will be produced for the mean. Additionally, a two-sided 95% confidence interval for the median will be reported, using nonparametric methods. Individual subject data listings will also be provided for this endpoint.

## 5 SAFETY ANALYSIS STRATEGY

### 5.1 Safety Endpoints

The safety endpoints are:

- Adverse events
- Device deficiencies

- Secondary surgical interventions
- Unplanned intraoperative surgical procedures

## **5.2 Safety Hypotheses**

There are no formal safety hypotheses in this study. The focus of the safety analysis will be a comprehensive descriptive assessment of safety endpoints listed in Section 5.1.

## **5.3 Statistical Methods for Safety Analyses**

The safety analysis set will be used for all safety analysis and will be based on the study eye unless otherwise stated.

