## 8 STUDY POPULATION

The study population will consist of male and female subjects (over the age of 18 years) with a diagnosis of age-related noncomplicated cataract (unilaterally). It is aimed to enroll (consent) approximately 120 subjects in up to 5 sites in the United States and/or Australia with a target of 100 subjects treated, with 10 to 40 subjects per site. Site-specific targets may vary based upon individual site capabilities and each site may include more than one surgeon. Each surgeon will perform at least 10 surgeries, but no more than 33% of the total subjects treated. Estimated time needed to recruit subjects for the study is approximately 5 months; however, unanticipated circumstances may shorten or lengthen this time and would not require amendment of this protocol. Because a 10% screening failure rate is expected and 10% for lost to follow-up, approximately 120 subjects are expected to be enrolled to ensure 100 completed subjects.

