### **10.4.2 Discontinuations**

Discontinued subjects are individuals who voluntarily withdraw or are withdrawn from the study by the investigator after signing informed consent, meeting eligibility criteria, and are exposed to IP.

Subject numbers of discontinued subjects must not be re-used (i.e., subject replacement is not allowed).

Subjects may discontinue from study or study treatment at any time for any reason. Subjects may also be discontinued from study treatment at any time if, in the opinion of the investigator, continued treatment poses a risk to their health.

For subjects choosing to discontinue from the study after exposure to IP, the investigator must complete all Exit procedures according to [Table 3–1](#) Schedule of Study Procedures and

Assessments, if the subject is willing and able, and if in the opinion of the investigator it is safe for the subject to do so.

The investigator must document the reason for study or treatment discontinuation in the subject's case history source documents.

To ensure the safety of all subjects who discontinue early, investigators must assess each subject and, if necessary, advise them of any therapies and/or medical procedures that may be needed to maintain their health.

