### ***Serious Adverse Events***

- Postoperative corneal incision site wound leakage
- Hypopyon
- Hyphema
- Toxic anterior segment syndrome
- Posterior capsular tear
- Vitreous prolapse
- Iridodialysis
- Posterior lens dislocation
- Chronic corneal edema (corneal stromal or epithelial swelling resulting in BCDVA of  $\leq 20/40$  at  $\geq 1$  month)
- Clinically significant cystoid macular edema
- Uncontrolled increase in IOP  $\geq 10$  mmHg over baseline and at least 25 mmHg
- Endophthalmitis
- Retinal detachment
- Pupillary block
- Suprachoroidal hemorrhage
- Vitreous hemorrhage
- Vision-threatening surgical problems
- Secondary surgical intervention (excluding posterior capsulotomy)

[figure not shown]
NOTE: Wound burps during the first week postoperatively, suture removal, planned blepharoplasty, and Nd:YAG capsulotomy (for PCO) are not considered adverse events for this study.

Any other potentially sight-threatening event may also be considered serious based on the judgment of the investigator and should be reported appropriately as delineated in Section [11.3](#).

AEs occurring in association with a device that is used in conjunction with the UNITY VCS (e.g., femtosecond laser) will be classified separately from those associated with the investigational device itself.

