### **5.3.1 Adverse Events**

All adverse events reported to Alcon will be accounted for in the reporting. Descriptive summaries (counts and percentages) and listings will be presented. The applicable definition of an adverse event is in the study protocol. A listing of all adverse events will be constructed to provide further details.

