### **5.3.3 Secondary Surgical Interventions**

Descriptive statistics (numbers and percentages) of eyes with secondary surgical interventions (SSI) will be presented. In addition, a listing of subjects with SSIs will be produced.

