## 5.4 Additional Safety Assessments

### 5.4.1 Visual Acuity

Best corrected distance visual acuity (BCDVA) is assessed at the screening, 1 week, and 1 month visits, and uncorrected distance visual acuity (UCDVA) is assessed at the 1 day visit, using a Snellen chart.

BCDVA will be converted to decimal VA by dividing the numerator by the denominator for the Snellen value. For example, 20/25 vision would be converted to a value of 0.8.

Observed decimal BCDVA values at each study visit and change from 1 month post-operative visit to screening values for the study eye will be presented descriptively (count, mean, median, standard deviation, minimum, and maximum). A categorical summary of Snellen values (not converted to decimal VA) will be produced and will include counts and percentages for each category at screening, 1 week and 1 month. A listing will be provided which presents BCDVA and UCDVA for all subjects at each visit.

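### Chronic corneal edema, which can be met only from 1 month, is reported over all treated eyes including those that left earlier, and the SAP gives no clear rule for tabulating Early Exit exams

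*SAP*

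**What the plan says.** **Denominator.** SAP 2.2 states: "The safety analysis set will include all eyes with attempted use of the UNITY VCS (successful or aborted after contact with the eye". SAP 5.3 adds: "The safety analysis set will be used for all safety analysis and will be based on the study eye unless otherwise stated". For adverse events, SAP 5.3.1 plans: "Descriptive summaries (counts and percentages) and listings will be presented". It names no other denominator, and neither it nor Protocol 12.6.1.2 sets a follow-up condition.

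**The event.** The list of serious adverse events in Protocol 11.1 includes "Chronic corneal edema (corneal stromal or epithelial swelling resulting in BCDVA of" 20/40 or worse, with a time criterion of 1 month or later.

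**Loss.** Protocol 8 sets enrolment at about 120 with this allowance: "Because a 10% screening failure rate is expected and 10% for lost to follow-up". SAP 6 repeats it.

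**Early Exit.** For subjects who leave after exposure, Protocol 10.4.2 says "the investigator must complete all Exit procedures according to" the schedule, provided the subject is willing and able and it is safe. Table 3-1 lists slit lamp, BCDVA, IOP and dilated fundus at Early Exit. In SAP 5.4.1 the Snellen category table "will include counts and percentages for each category at screening, 1 week and 1 month". Decimal BCDVA, IOP and slit lamp grading (SAP 5.4.1 to 5.4.3) are summarised by visit, in sections that name only the scheduled visits. SAP 1.2 says that early exit visits are included where appropriate, without saying how.

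**The concern.** A percentage is easiest to interpret when every eye in its denominator could have been counted in its numerator. For chronic corneal edema that fails: an eye last seen in the second week adds to the denominator and can never add to the numerator. The reported rate is then lower than the rate among eyes in which the question was answered.

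There is no control arm to share this effect and no safety hypothesis. The descriptive percentages are the safety result, and Protocol 7.2 intends to set them beside existing evidence on cataract surgery. A shortfall in an SAE rate would favour the device.

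The second issue concerns data already collected. Without a rule for Early Exit exams, some will appear in listings only, or their placement will be settled after the data have been seen.

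**Working it through.** **1. The plan's own figures.** The documents give no figure for safety percentages. The figures they do give reproduce:
- Half-width at p = 50%: 1.96 × √(0.5 × 0.5 / 100) = 0.098, below 10%.
- Enrolment: 100 × (1 + 0.10 + 0.10) = 120.

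**2. Eyes that cannot be cases.** Inputs are 120 enrolled, 10% screen failure and 10% lost. Assumption: all the loss falls after surgery and before the 1-month exam.
- Treated: 120 × 0.90 = 108.
- Assessed at 1 month: 108 × 0.90 = 97.2, about 97.
- Not assessed: 108 − 97 = 11.

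**3. Effect on the percentage.** With x events, the planned figure is x/108 and the figure in eyes assessed is x/97. Their ratio is 97/108 = 0.898, about 0.90. The event counts below are illustrative assumptions.

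| x | x/108 (exact 95% upper limit) | x/97 (exact 95% upper limit) | Difference, points |
|---|---|---|---|
| 0 | 0.00% (3.36%) | 0.00% (3.73%) | 0 |
| 1 | 0.93% (5.05%) | 1.03% (5.61%) | 0.1 |
| 3 | 2.78% (7.90%) | 3.09% (8.77%) | 0.3 |
| 5 | 4.63% (10.47%) | 5.15% (11.62%) | 0.5 |

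**4. Other readings of the loss.** Protocol 8 gives 100 both as the number treated and as the number completed, so the base is uncertain.
- 110 treated, 100 assessed: 100/110 = 0.909.
- 112 treated, 100 assessed (100/0.9 = 111.1, rounded up): 100/112 = 0.893.
- 100 treated, 90 assessed: 90/100 = 0.900.

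For a general loss fraction L the ratio is 1 − L: 0.95 at an assumed 5% and 0.85 at an assumed 15%.

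**5. Outer bound.** If all 11 unseen eyes had the event, the rate would be (x + 11)/108: 10.2% for x = 0 and 14.8% for x = 5. This shows how much is unknown; it is not a forecast.

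**6. Where an Early Exit exam goes.**
- Snellen category table: limited to three named visits, so Early Exit BCDVA is left out.
- Decimal BCDVA, IOP and slit lamp grading: ambiguous. Early Exit is a column of the schedule, but these sections do not mention it.
- Fundus: a listing only, for every eye, so nothing is lost that is specific to early leavers.
- Visit windows: 1 Week is Day 4 to 10 and 1 Month is Day 28 to 42. Days 11 to 27 lie in neither, so an exit exam on Day 15 has no window.

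**The case against.** The strongest reply is that this is a small matter of presentation in a descriptive feasibility study. The 1-month corneal edema grading and 1-month BCDVA categories already describe the eyes seen at 1 month. Protocol 12.6.1.2 requires the sample size with each categorical summary, and SAP 3 reports disposition, so a reader can see how many eyes left. A difference of 0.1 to 0.5 points is also far smaller than the sampling error: with 3 events in 108 the exact upper limit is 7.90%. All of this stands, and it sets the priority. It does not supply the missing denominator for the SAE itself.

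A reader might infer more than the documents support:
- **That early leavers lower all adverse event rates by construction.** Events recorded before or at exit are counted. Device deficiencies are reported as counts, and intraoperative procedures are complete at surgery. Other postoperative events may be missed when follow-up is short, but their definitions do not prevent an early leaver from being a case.
- **That cystoid macular edema has the same problem.** Its entry in Protocol 11.1 carries no time criterion.
- **That early edema goes unrecorded.** Protocol 11.3 exempts it only if it can be expected to resolve within 2 weeks without lasting visual effect, and its grade is tabulated at the visits attended.
- **That Early Exit exams enter no visit summary.** This is firm only for the Snellen category table. SAP 1.2 and the by-visit wording leave room for them elsewhere, and an exit on Day 5 falls inside the 1 Week window.
- **That the comparison with outside evidence is shown to be biased.** Protocol 7.2 names no comparator rate or denominator, so no mismatch can be demonstrated.

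It is also fair that SAP 5.3.1 does not write out its denominator. The safety set is inferred from SAP 5.3, which supplies no other.

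**Conclusion.** The point holds for one event and one table, with an ambiguity beside them. For chronic corneal edema, eyes that leave before the 1-month exam are counted as non-cases although they cannot meet the definition. The percentage is about 0.90 of that in eyes assessed (0.89 to 0.91 across readings of the allowance), or 0.1 to 0.5 points for an assumed 1 to 5 events.

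This rests on three assumptions: the 10% loss falls after surgery, the safety set is the denominator, and loss is unrelated to outcome if the rate in assessed eyes is to stand for all treated eyes.

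The Snellen category table omits the required Early Exit BCDVA, and the SAP is unclear for decimal BCDVA, IOP and slit lamp grading. The 10% allowance does not size this second part, because subjects who are truly lost may have no exit exam. Minor priority.

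**What to change.** **SAP 5.3.1.** Keep the safety-set percentage for chronic corneal edema. Beside it, give the percentage with eyes examined on or after Day 28, or with the event, as the denominator. State the number of safety-set eyes without a 1-month exam.

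**SAP 5.4.1 to 5.4.3.** Leave the 1-month column unchanged. Add a separate column for the last postoperative exam (1 month or Early Exit), with the day of exam. This gives exits on Days 11 to 27 a stated place.

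**Cost.** SAP wording and a few table columns, from data already scheduled. Two denominators need a footnote, and the rate for this event may look slightly less favourable. The added column mixes exam days, so it is supportive only. An examined-eyes denominator does not remove bias if leaving is related to outcome, which is why the count of unexamined eyes should stand next to it.

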### **5.3.1 Adverse Events**

All adverse events reported to Alcon will be accounted for in the reporting. Descriptive summaries (counts and percentages) and listings will be presented. The applicable definition of an adverse event is in the study protocol. A listing of all adverse events will be constructed to provide further details.

### **5.3.2 Device Deficiencies**

The applicable definition of a device deficiency is in the study protocol. A frequency table showing counts for each device deficiency category will be presented. In addition, a listing of all device deficiencies will be provided.

### **5.3.3 Secondary Surgical Interventions**

Descriptive statistics (numbers and percentages) of eyes with secondary surgical interventions (SSI) will be presented. In addition, a listing of subjects with SSIs will be produced.

### **5.3.4 Unplanned intraoperative surgical procedures**

Unplanned intraoperative surgical procedures that occur during the cataract surgery will be reported. Descriptive statistics will be presented for these procedures and a listing will be constructed.

## 5.4 Additional Safety Assessments

### 5.4.1 Visual Acuity

Best corrected distance visual acuity (BCDVA) is assessed at the screening, 1 week, and 1 month visits, and uncorrected distance visual acuity (UCDVA) is assessed at the 1 day visit, using a Snellen chart.

BCDVA will be converted to decimal VA by dividing the numerator by the denominator for the Snellen value. For example, 20/25 vision would be converted to a value of 0.8.

Observed decimal BCDVA values at each study visit and change from 1 month post-operative visit to screening values for the study eye will be presented descriptively (count, mean, median, standard deviation, minimum, and maximum). A categorical summary of Snellen values (not converted to decimal VA) will be produced and will include counts and percentages for each category at screening, 1 week and 1 month. A listing will be provided which presents BCDVA and UCDVA for all subjects at each visit.

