## **10.2.8 Best Corrected Distance Visual Acuity: Safety Assessment**

Snellen visual acuity testing with manifest refraction must be performed prior to any assessment requiring administration of eye drops to dilate the eye, or any assessment requiring contact with the eye.

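### SAP 5.4.1 summarises BCDVA and its change on the decimal scale, whose steps are unequal: mean acuity reads slightly too well, and losses from poorer starting acuity are compressed

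*SAP*

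**What the plan says.** Protocol 10.2.8 sets the measurement: "Snellen visual acuity testing with manifest refraction must be performed". Both schedules of assessments place BCDVA at screening, 1 week and 1 month (and at early exit), by the site's standard of care.

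SAP 5.4.1 then sets the analysis: "BCDVA will be converted to decimal VA by dividing the numerator by the denominator for the Snellen value". It gives an example: "For example, 20/25 vision would be converted to a value of 0.8". The quantities summarised are "Observed decimal BCDVA values at each study visit and change from 1 month post-operative visit to screening values for the study eye", each with count, mean, median, standard deviation, minimum and maximum. No log-scale summary is named.

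Two other outputs are planned in the same section:

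- for the three scheduled BCDVA visits, "A categorical summary of Snellen values (not converted to decimal VA) will be produced and will include counts and percentages for each category";
- every subject's corrected and uncorrected acuity, listed visit by visit.

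BCDVA falls under SAP 5.4, the additional safety assessments. The safety endpoints in SAP 5.1 are adverse events, device deficiencies, secondary surgical interventions and unplanned intraoperative procedures. SAP 5.2 states no safety hypothesis.

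**The concern.** Decimal acuity is the reciprocal of relative letter size. A line near 20/20 takes up far more of the scale than a line in a poor eye, and two consequences follow for the planned table.

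First, the arithmetic mean of a reciprocal is pulled towards the best eyes, so mean acuity at a visit reads better than it would on a scale with equal steps.

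Second, the change weights an eye by where it started as well as by how much vision it lost. No inclusion or exclusion criterion in Protocol 8.1 or 8.2 limits screening BCDVA, so starting acuity can vary, and the unequal steps matter most when it does. The minimum and median of the change do not escape this, because the scale can reorder losses.

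What is at stake is how well a descriptive safety table can be read. Protocol 7.2 defends the single-arm design on the ground that results can be set against existing evidence. A mean that reads slightly too well, with no count of eyes that lost vision, serves that purpose less well than it could.

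**Working it through.** **Inputs.** The conversion rule and its example come from SAP 5.4.1. LogMAR = log10(denominator/numerator), and 0.1 logMAR is taken as one line. Change is taken as 1 month minus screening, so a loss is negative in decimal. The SAP's phrase could be read with the opposite sign; that would swap minimum and maximum but leave the scale problem unchanged. The documents give no BCDVA distribution, so every mix below is an assumption.

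**The plan's own figure.** 20/25 = 0.80, which reproduces the SAP's example.

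**Unequal steps and reordered losses.** Decimal change = 20/(1-month denominator) - 20/(screening denominator). LogMAR loss = log10(1-month denominator / screening denominator).

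| Loss | Decimal change | LogMAR loss | Lines |
|---|---|---|---|
| 20/20 to 20/25 | 0.80 - 1.00 = -0.20 | 0.097 | 1 |
| 20/40 to 20/50 | 0.40 - 0.50 = -0.10 | 0.097 | 1 |
| 20/100 to 20/200 | 0.10 - 0.20 = -0.10 | 0.301 | 3 |
| 20/20 to 20/40 | 0.50 - 1.00 = -0.50 | 0.301 | 3 |
| 20/40 to 20/200 | 0.10 - 0.50 = -0.40 | 0.699 | 7 |
| 20/20 to 20/200 | 0.10 - 1.00 = -0.90 | 1.000 | 10 |

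If only the fourth and fifth losses occurred, the minimum of the change would be -0.50. That value belongs to the eye that lost 3 lines, not the eye that lost 7.

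From a common start the order is kept but the gap shrinks. 20/20 to 20/200 against 20/20 to 20/25 is 0.90/0.20 = 4.5 times on the decimal scale, and 1.000/0.0969 = 10.3 times in logMAR.

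**Mean acuity at one visit.** The back-converted logMAR mean, 10^(-mean logMAR), is the geometric mean of the decimals. The arithmetic mean is never below the geometric mean, so the direction is fixed. The gap in lines is 10 x (mean logMAR + log10(decimal mean)).

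| Assumed 100 eyes | Decimal mean | LogMAR mean | Gap (lines) |
|---|---|---|---|
| A. Post-operative: 60, 25, 10, 5 at 20/20, 20/25, 20/32, 20/40 | 0.888 (20/22.5) | 0.060 (20/22.9) | 0.08 |
| B. As A, with the 5 worst eyes at 20/200 | 0.868 (20/23.1) | 0.095 (20/24.9) | 0.33 |
| C. Screening: 15, 25, 20, 15, 10, 7, 5, 3 at 20/32, 20/40, 20/50, 20/63, 20/80, 20/100, 20/200, 20/400 | 0.392 (20/51.0) | 0.458 (20/57.5) | 0.52 |
| D. 90 at 20/20, 10 at 20/200 | 0.91 (20/22) | 0.10 (20/25) | 0.6 |
| E. Screening: 40, 30, 15, 10, 5 at 20/40, 20/63, 20/100, 20/200, 20/400 | 0.338 (20/59) | 0.54 (20/69) | 0.7 |
| F. 50 at 20/20, 50 at 20/200 (extreme) | 0.55 (20/36.4) | 0.50 (20/63.2) | 2.4 |

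For D: (90 x 1.0 + 10 x 0.1)/100 = 0.91, and (90 x 0 + 10 x 1.0)/100 = 0.10.

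**Improvement between visits.**

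- C to A: the decimal means imply 10 x log10(0.888/0.392) = 3.6 lines. LogMAR gives (0.458 - 0.060) x 10 = 4.0.
- E to D: the decimal means imply 10 x log10(0.91/0.338) = 4.3 lines. LogMAR gives (0.54 - 0.10) x 10 = 4.4.

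The more widely spread screening values are flattered more, so in these mixes the decimal scale understates improvement.

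**The case against.** The strongest reply is that little depends on this table. BCDVA is not a listed safety endpoint, nothing is tested, and the gap in mean acuity is under one line in every assumed mix except the deliberately extreme one. The median of the observed values hardly depends on the scale. The Snellen categories are unconverted, and the listing shows every eye at every visit. Protocol 11.2 requires clinically relevant untoward changes in study parameters to be reported as adverse events. Protocol 11.1 makes sight-threatening problems, and chronic corneal edema defined by a BCDVA threshold, reportable as serious. All of this stands, and it limits the size of the point.

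It does not remove the point. The median and minimum of the change do depend on the scale. The categorical table shows each visit separately, so a reader who wants to know how many eyes lost vision must count them from the listing.

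A reader might infer more than the documents support:

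- *A severe loss counts about the same as a mild one.* This holds only when the severe loss starts from poorer acuity. From the same start it is compressed, not equated.
- *The decimal scale flatters the improvement after surgery.* The upward shift applies to the mean at a visit. The mean change may be understated.
- *Severe losses will be hidden.* The categories, the listing and the adverse event rules keep them visible.
- *Off-chart eyes will drop out of the mean.* An acuity recorded without a fraction cannot be divided, SAP 5.4.1 gives no rule for it, and Protocol 12.5 plans no imputation. But it is not known that such records will occur, and the Manual of Procedures, which holds the detailed assessment descriptions, is not available here.
- *Comparison with outside evidence is compromised.* Protocol 7.2 names neither BCDVA nor a scale, so this cannot be shown.

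**Conclusion.** The point holds as a minor one about reporting. The mean, SD and change of BCDVA are computed on a scale without equal steps. The direction of the effect on mean acuity at a visit is certain. Its size, about 0.1 to 0.7 line in mixes A to E, rests entirely on assumed distributions. The compression and possible reordering of losses follow from arithmetic alone, but they affect the actual table only if eyes that start from different acuities lose vision. Since no conclusion of the study is tested on BCDVA, the case for change is that the better summary costs almost nothing.

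**What to change.** In SAP 5.4.1:

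1. Derive logMAR = log10(denominator/numerator) for each BCDVA. Compute count, mean, SD, median, minimum, maximum and the change between screening and 1 month on that scale. State that change is 1 month minus screening, so that a positive logMAR value is a loss.
2. Present the means back-converted to Snellen or decimal for readers who prefer those units.
3. Add the number and percentage of eyes whose 1-month BCDVA is worse than screening by at least 0.1 and by at least 0.2 logMAR. Apply the thresholds to the change rounded to one decimal. Otherwise a one-line loss such as 20/20 to 20/25, which is 0.097, would be missed.
4. If any off-chart acuity is recorded, report the count beside the summary at that visit so that it is not dropped silently.

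Keep the Snellen categories and the listing as planned. The cost is SAP wording and one derived variable, with no new data. Mean acuity will read slightly less favourably.
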